## **10.8 Interim analysis**

No interim analysis is planned.

# **11 Ethical considerations**

## **11.1 Regulatory and ethical compliance**

This clinical study was designed and shall be implemented and reported in accordance with the ICH Harmonized Tripartite Guidelines for Good Clinical Practice, with US Code of Federal Regulations Title 21, and with the ethical principles laid down in the Declaration of Helsinki.

## **11.2 Informed consent procedures**

Eligible patients may only be included in the study after providing written (witnessed, where required by law or regulation), Institutional Review Board (IRB)-approved informed consent. Informed consent must be obtained before conducting any study-specific procedures (i.e. all of the procedures described in the protocol). The process of obtaining informed consent should be documented in the patient source documents.

The investigator and the study team will prepare the informed consent form that complies with the ICH GCP guideline and regulatory requirements and is considered appropriate for this study.

Women of child bearing potential should be informed that taking the study medication may involve unknown risks to the fetus if pregnancy were to occur during the study and agree that in order to participate in the study they must avoid pregnancy for the duration of the study. If there is any question that the patient will not reliably comply, they should not be entered in the study.

## **11.3 Responsibilities of the investigator and IRB**

The protocol and the proposed informed consent form must be reviewed and approved by IRB before study start. Prior to study start, the investigator is required to sign a protocol signature page confirming his agreement to conduct the study in accordance with these documents and all of the instructions and procedures found in this protocol and to give access to all relevant data and records to designated agents of Novartis, IRBs, and regulatory authorities as required. If an inspection of the clinical site is requested by a regulatory authority, the investigator must inform Novartis immediately that this request has been made.

## **11.4 Publication of study protocol and results**

The study team assures that the key design elements of this protocol will be posted in a publicly accessible database such as clinicaltrials.gov. In addition, upon study completion and finalization of the study report the results of this trial will be either submitted for publication and/or posted in a publicly accessible database of clinical trial results.

## 12 Protocol adherence

Investigators ascertain they will apply due diligence to avoid protocol deviations. If the investigator feels a protocol deviation would improve the conduct of the study this must be considered a protocol amendment, and unless such an amendment is agreed upon by Novartis and approved by the IRB it cannot be implemented. All major protocol deviations will be recorded and reported to the IRB.

### 12.1 Protocol Amendment

Any change or addition to the protocol can only be made in a written protocol amendment that must be approved by the IRB. Notwithstanding the need for approval of formal protocol amendments, the investigator is expected to take any immediate action required for the safety of any patient included in this study, even if this action represents a deviation from the protocol. In such cases, Novartis and IRB should be notified of this action within 10 working days.

## Appendix 1: Clinically notable laboratory values and vital signs

Table 13-1 Criteria for notable abnormalities

Chemistry parameters	Standard units	SI units
Liver function and related variables		
AST (SGOT)	$\geq 3 \times$ ULN	$\geq 3 \times$ ULN
ALT (SGPT)	$\geq 3 \times$ ULN	$\geq 3 \times$ ULN
Bilirubin	$\geq 3 \times$ ULN	$\geq 3 \times$ ULN
Alkaline phosphatase	$\geq 3 \times$ ULN	$\geq 3 \times$ ULN
Renal function, metabolic and electrolyte variables		
Urea	None	None
Creatinine	30% above baseline	30% above baseline
Uric acid	M $\geq 12$ mg/dL F $\geq 9$ mg/dL	M $\geq 714$ $\mu$ mol/L F $\geq 535$ $\mu$ mol/L
Glucose	<45 mg/dL or $>250$ mg/dL	<2.5 mmol/L or $>13.9$ mmol/L
Cholesterol	$\geq 350$ mg/dL	$\geq 9.1$ mmol/L
Triglycerides	$\geq 750$ mg/dL	$\geq 8.5$ mmol/L
CPK (MB)	None	None
Potassium	$\leq 3.0$ mEq/L $\geq 6.0$ mEq/L	$\leq 3$ mmol/L $\geq 6$ mmol/L
Magnesium	<0.97 mg/dL or $>3.65$ mg/dL	<0.4 mmol/L or $>1.5$ mmol/L
Calcium	$\leq 6$ mg/dL or $\geq 13$ mg/dL	$\leq 1.5$ mmol/L or $\geq 3.2$ mmol/L
Phosphate	None	None
Amylase	$\geq 2 \times$ ULN	$\geq 2 \times$ ULN
Lipase	$\geq 2 \times$ ULN	$\geq 2 \times$ ULN
Hematology parameters		
Hemoglobin	<7 g/dL	<4.39 mmol/L
Platelets (thrombocytes)	$<50$ k/mm  $\geq 700$ k/mm 	$<50 \times 10^9$ /L $\geq 700 \times 10^9$ /L
Leukocytes (WBCs)	$\leq 2.0$ k/mm  or $\geq 16$ k/mm 	$\leq 2.0 \times 10^9$ /L or $\geq 16 \times 10^9$ /L
Granulocytes (neutrophils)	$\leq 1,000$ /mm 	$\leq 1 \times 10^9$ /L
Eosinophils	$\geq 12\%$	$\geq 12\%$
Lymphocytes	$\leq 1,000$ /mm 	$\leq 1 \times 10^9$ /L
Urinalysis		
Protein/creatinine	<200 mg/g	<22.7 mg/mmol
Vital sign variables		
Pulse (beats/min.)	None	
Systolic BP (mm/Hg)	Either an increase of $\geq 30$ that results in $\geq 180$ or $>200$ (mm/Hg) or Either a decrease of $\geq 30$ that results in $\leq 90$ or $<75$ (mm/Hg)	

Diastolic BP (mm/Hg)	Either an increase of $\geq 20$ that results in $\geq 105$ or $> 115$ (mm/Hg) or Either a decrease of $\geq 20$ that results in $\leq 50$ or $< 40$ (mm/Hg)
----------------------	---

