### **3.2 Secondary objectives**

The key secondary objective is to compare renal function of the everolimus treatment arms to the MMF/MPA treatment arm at 12 and 24 months post-transplantation. Renal function will be measured by the calculated glomerular filtration rate (GFR), using the MDRD (Modification of Diet in Renal Disease) formula (20).

Other secondary objectives include:

- The incidence of treated BPAR at 12 months
- The incidence of graft loss at 12 months
- The incidence of death or loss to follow up at 12 months
- Incidence of adverse events (AEs)
- Incidence of serious adverse events (SAEs)
- Incidence of new onset diabetes mellitus defined as non-diabetic patients before transplantation, who are receiving glucose lowering treatment for more than 30 days

post-transplant, or with a random plasma glucose  $\geq 200$  mg/dL (11.1 mmol/L) with 2 fasting plasma glucose values  $\geq 126$  mg/dL (7 mmol/L).

- Incidence of CMV (viremia or viruria) and BKV (viremia or viruria)
- Incidence of proteinuria by more than 3 fold or proteinuria reaching 1.5gm/day
- The comparison of the health related quality of life for patients treated with everolimus plus low dose tacrolimus to CellCept plus standard dose tacrolimus

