#### **4 Study Design**

This is a 24 month, Single Center, Open-Label, Randomized, Parallel assignment, non-inferiority pilot study of safety and efficacy, comparing Everolimus with low-dose Tacrolimus (2 arms; 1 arm will involve a conversion to MMF/MPA at month 3) and the standard of care (with standard dose Tacrolimus and MMF/MPA) in recipients of DCD and elevated KDPI kidneys. For this study, either MMF 1,000 mg BID or MPA 720 mg BID will be allowed since MMF and MPA are considered to be therapeutically equivalent.

All study patients must give a signed informed consent voluntarily prior to any study-related activities. Once a signed consent is obtained, baseline assessment including laboratory testing will take place to determine patient's eligibility to participate in the study. Baseline assessments will occur in the time period starting 3 weeks pre-transplantation and ending at the time of transplantation. Eligible patients will receive Campath or Simulect as an induction therapy according to the institutional practice.

Randomization will occur within 24-hour of transplantation. Fifty patients who meet the inclusion/exclusion criteria will be randomized to receive their first dose of study drug (0.75 mg Everolimus (2 arms) or 1,000/720 mg MMF/MPA) within 24 hours of transplantation (Figure 4-1). The first dose of Tacrolimus will be given to all study participants according to our standard practice. Patients will be assigned to either continuation on low-dose Tacrolimus (Arm 1), to conversion from low-dose Tacrolimus to Mycophenolate at month 3 (Arm 2), or to standard therapy with Tacrolimus and Mycophenolate (Arm 3).

Everolimus and Tacrolimus levels will be monitored throughout the study, and respective doses will be adjusted according to the desired trough levels. Patients will be started on 0.75mg BID. Everolimus will be dosed to target trough levels of 3 to 8 ng/ml, starting on Day 7.

Earlier increase in Everolimus level may decrease Tacrolimus exposure, which may lead to under-immunosuppression; increasing the risk of acute rejection (16). Therefore, Day 7 $\pm$ 1 was chosen to initiate the first dose adjustment for Everolimus after careful consideration of the half-life of this drug and turnaround time of the trough level availability. The target Everolimus trough level was determined based on the Novartis B201 and B251 studies (17).

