## **7.2 Patient demographics/other baseline characteristics**

After informed consent has been signed and the patient's eligibility to participate in the study has been determined, baseline patient information will be obtained, such as date of birth, age, sex, race, full relevant medical history/current medical conditions, information on renal transplantation background of recipient and donor and on transplantation procedure.

Baseline assessments will occur in the time period starting 30 days pre-transplantation and ending at the time of transplant. Results of a physical examination at a baseline, include pregnancy test (within 48 hours prior to transplantation), vital signs, blood chemistry and hematology, urinalysis, including a quantitative protein/creatinine ratio.

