### **7.5.8 Clinical chemistry**

Sodium, potassium, chloride, calcium, magnesium, inorganic phosphate, blood urea nitrogen, creatinine, glucose, uric acid, AST, ALT, alkaline phosphatase, total bilirubin, total cholesterol, HDL, LDL, triglycerides, CPK, lipase, and amylase will be assessed at hospital affiliated laboratory. The blood chemistry will be measured at Baseline, on Day 1, 3, and 5; Weeks 1, 2, and 4; Months 2, 3, 4, 6, 8, 10, 12, 15, 18, 21, and 24. LDL and HDL will be measured only at Baseline, Week 4, Months 6 and 12.

Random or fasting plasma glucose values as needed to rule out or confirm suspected new onset of diabetes.

If the CPK level is above the upper limit of normal, CK-MB fraction will be measured.

If the total bilirubin concentration is greater than 1.5 times the upper limit of normal, total bilirubin should be differentiated into the direct and indirect reacting bilirubin.

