### **7.5.9 Urine measurements**

Measurements will be taken for glucose, protein and quantitative protein/creatinine ratio by a mid-stream urine sample at Baseline, Day 1, 3, and 5; Weeks 1, 2, and 4; Months 2, 3, 4, 6, 8, 10, 12, 15, 18, 21, and 24.

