### **10.5.2 Safety**

Safety variables to be assessed include discontinuation from study, discontinuation from treatment, renal function, AE/infection, SAE, notable events, laboratory tests, and vital signs.

Comparison of calculated GFR using an analysis of covariance (ANCOVA) with baseline (Month 1) GFR as a covariate, and treatment and induction therapy as main effects, will be performed. Month 24 GFRs will be divided into three categories (<30, 30-60, >60) to classify chronic kidney disease. The proportion of patients in certain categories will be compared between treatment groups using the Cochran-Mantel-Haenszel test controlling for the Month 1 category.

Other safety variables include incidences of AEs, SAEs, new onset diabetes mellitus, CMV, BKV and proteinuria. These incidences will be compared between treatment groups using a Cochran-Mantel-Haenszel test, stratified by induction therapy. Urine protein/creatinine ratios will be compared between treatment groups using the Wilcoxon Rank-Sum test.

Additional assessments of safety will be based on the frequency of adverse events and on the number of laboratory values that fall outside of pre-determined notable ranges. Other safety data (e.g. vital signs and special tests) will be considered as appropriate. The data collected will be presented in listings, summary tables and graphs. All analyses will be performed on the SS.

Adverse events will be summarized by presenting, for each treatment group, the number and percentage of patients having any adverse event, having an adverse event in each body system and having each individual adverse event. The same type of summaries will be provided for serious adverse events and for events suspected to be related to the study medication. Any other information collected (e.g. severity or relatedness to study medication) will be listed as appropriate.

Laboratory data will be summarized by presenting shift tables using notable ranges (baseline to most extreme post-baseline value), by presenting summary statistics of raw data and change from baseline values (means, medians, standard deviations, ranges) and by the flagging of notable values in data listings.

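### The creatinine notable-value flag is referenced to a pre-transplant baseline and so hardly responds to graft decline; the proteinuria event lacks both a reference value and a matching measurement

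*Combined protocol and SAP*

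**What the plan says.** Appendix 1 (Table 13-1) gives the notable criterion for creatinine as "30% above baseline". It is the only laboratory row in that table set relative to baseline, and the appendix does not define the term.

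Two sections do. Section 4: "Baseline assessments will occur in the time period starting 3 weeks pre-transplantation and ending at the time of transplantation". Section 7.2 gives a slightly different window: "Baseline assessments will occur in the time period starting 30 days pre-transplantation and ending at the time of transplant". Both end at the transplant. Section 7.2 includes in that baseline "vital signs, blood chemistry and hematology, urinalysis, including a quantitative protein/creatinine ratio". Section 7.5.8 then lists Baseline as a separate time point ahead of the post-operative days: "The blood chemistry will be measured at Baseline, on Day 1, 3, and 5".

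Section 10.5.2 rests part of the safety assessment "on the number of laboratory values that fall outside of pre-determined notable ranges". It also calls for flagged listings and for shift tables from baseline to the most extreme later value. For GFR alone, the same section takes Month 1 as baseline.

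On urine protein, section 3.2 lists the outcome "Incidence of proteinuria by more than 3 fold or proteinuria reaching 1.5gm/day". Section 7.5.9 supplies the data: "Measurements will be taken for glucose, protein and quantitative protein/creatinine ratio by a mid-stream urine sample at Baseline", and then at the scheduled visits through Month 24. Section 7.4.6 confirms that proteinuria is determined from a spot ratio. Section 10.5.2 compares the incidence of proteinuria by a Cochran-Mantel-Haenszel test and the ratios by a Wilcoxon rank-sum test.

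**The concern.** Creatinine before a kidney transplant reflects the failing native kidneys or, in second transplants, a failed earlier graft. Once the new graft works, creatinine should settle well below that level. A threshold of 130% of the pre-transplant value therefore sits far above the range in which a functioning graft deteriorates.

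The shift table has a further weakness. Post-baseline values start at Day 1, so a patient's most extreme creatinine may simply be an early peri-transplant value, which says little about later decline.

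The rationale for the everolimus arms is to spare vulnerable kidneys from calcineurin-inhibitor toxicity, so renal safety output is what readers will look at. A creatinine table showing few notable values in any arm could be read as reassurance when the criterion could hardly have been met.

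The proteinuria event has a different problem. Two analysts with the same data could count different events, because the reference for the 3-fold rise and the route from a spot ratio to g/day are both left open.

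**Working it through.** The plan states no figure to reproduce here, so the check is direct arithmetic on its criteria. Pre-transplant creatinine B, stable graft creatinine G and reference protein/creatinine ratio P are assumptions, because the documents give none of them.

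**Creatinine, reference as written.** Flag level = 1.3 × B. Fold rise needed from a stable graft = 1.3 × B / G.

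| B (mg/dL) | Flag (mg/dL) | G = 1.2 | G = 1.5 | G = 2.0 | G = 2.5 |
|---|---|---|---|---|---|
| 4 | 5.2 | 4.33 | 3.47 | 2.60 | 2.08 |
| 6 | 7.8 | 6.50 | 5.20 | 3.90 | 3.12 |
| 8 | 10.4 | 8.67 | 6.93 | 5.20 | 4.16 |
| 10 | 13.0 | 10.83 | 8.67 | 6.50 | 5.20 |
| 12 | 15.6 | 13.00 | 10.40 | 7.80 | 6.24 |

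The required rise runs from 1.3 × 4 / 2.5 = 2.08 to 1.3 × 12 / 1.2 = 13. Every cell exceeds 2, so a doubling is missed throughout. The margin is thin only in the top right corner, where doubling 2.5 gives 5.0 against a flag at 5.2.

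*Break-even.* A doubling reaches the flag when 2G ≥ 1.3B, that is B ≤ 1.54 × G. For G = 1.5 this needs B ≤ 2.3 mg/dL; for G = 2.5 it needs B ≤ 3.8 mg/dL. The conclusion therefore depends on pre-transplant values being above those levels.

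**Creatinine, Month 1 reference.** Flag level = 1.3 × G. For G of 1.2, 1.5, 2.0 and 2.5 the flag falls at 1.56, 1.95, 2.60 and 3.25 mg/dL, a 1.3-fold rise in every case.

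**Proteinuria.** If 1 g/g is taken as about 1 g/day, the effective threshold is the lower of 3 × P and 1.5.

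- P = 0.1: 3 × 0.1 = 0.3, so the event is met above 0.3.
- P = 0.2: threshold 0.6.
- P = 0.3: threshold 0.9.
- P = 0.5: 3 × 0.5 = 1.5, so the two limbs coincide.
- P above 0.5: the 1.5 limb always decides.

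The choice of reference thus matters for patients with a low ratio. A patient passing no urine before transplant has no pre-transplant ratio to multiply, though the absolute limb could still classify that patient once a conversion is stated.

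**The case against.** The strongest reply is that graft decline is well covered elsewhere. Section 7.4.3 calls for biopsy in renal dysfunction and suspected rejection. Section 7.5.6 sends extreme laboratory values to the investigator. Section 8.1 makes clinically significant laboratory abnormalities adverse events. The data monitoring committee reviews laboratory safety data (section 8.4). Section 10.5.2 analyses GFR by ANCOVA against Month 1 and by Month 24 category, and graft loss is a component of the primary endpoint. All of this stands. A reader might infer that graft deterioration would go undetected; the documents do not support that. What is lost is the information in one set of safety tables.

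Nor can it be said that the flag would stay silent in every arm. The protocol anticipates delayed graft function, and early values in such patients could exceed 130% of the pre-transplant value.

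On proteinuria, three stronger readings fail.

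- That the 3-fold rise is measured from pre-transplant urine: section 3.2 names no reference, and section 7.5.9 schedules many later ratios. The defect is a missing reference.
- That the objective is not measured: the ratio is collected throughout, and the Wilcoxon comparison needs no baseline.
- That heavy pre-transplant proteinuria would mask graft proteinuria: the event has an absolute limb, which decides whenever the reference is above 0.5 g/g on the stated approximation.

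What remains is that the incidence tested by Cochran-Mantel-Haenszel cannot be classified unambiguously. The Wilcoxon test on the ratios, which names no time point, does not settle that.

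**Conclusion.** The creatinine point holds. Followed as written, the criterion compares the graft with a value from before it functioned. It then needs a 2.1- to 13-fold rise under the assumed ranges (4 to 12 mg/dL before transplant, 1.2 to 2.5 mg/dL stable graft) and misses a doubling throughout. This rests on reading baseline in Appendix 1 as sections 4, 7.2 and 7.5.8 define it, which is the ordinary reading. Section 10.5.2 already moves to Month 1 for GFR, which is calculated from the same creatinine, without saying whether Appendix 1 follows.

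The effect is confined to the notable-value counts, listings and shift table; the primary endpoint and the eGFR comparisons are untouched. The proteinuria point is secondary: an undefined reference and no stated conversion from spot ratio to g/day. Both are worth settling before the data are analysed, because in an open-label trial a later choice of reference could look data-driven.

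**What to change.** **Creatinine.** In Table 13-1 and section 10.5.2, for visits after Month 1, base the creatinine flag and shift table on the Month 1 (Day 28) value, and report earlier visits separately. State what is done when the Day 28 value is missing.

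**Proteinuria.** In sections 3.2 and 10.5.2, define the event on the measured spot protein/creatinine ratio, for example at least 1.5 g/g as the approximation of 1.5 g/day. Use the Month 1 ratio as the reference for the 3-fold limb.

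**Same table.** The protein/creatinine row is printed as notable below 200 mg/g, which flags low rather than high values. Check its direction.

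**Cost.** Wording only; creatinine and the ratio are already scheduled at Day 28 and later visits. More creatinine values will be flagged, and g/g only approximates g/day. A graft still recovering at Day 28 will carry a high reference, and a post-randomization reference may already differ by arm. The plan accepts the same limits for its GFR baseline.

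These are reporting and endpoint definitions and do not change patient management. The follow-up text on premature discontinuation in section 7.5 also speaks of clinically notable abnormalities, so the sponsor should say whether that clause relies on Table 13-1.

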## Appendix 2: Banff '97 Classification of renal allograft rejection

### Banff '97 diagnostic categories for renal allograft biopsies

1. Normal
2. Antibody-mediated rejection - Rejection demonstrated to be due, at least in part, to documented anti-donor antibody ("suspicious for" if antibody not demonstrated)
  - Type I – ATN – like – C4d+, minimal inflammation
  - Type II – Capillary-margination and/or thromboses, Ig and/or C4d+
  - Type III – Arterial – v3, C4d+
3. Borderline changes ("suspicious" for acute cellular rejection). This category is used when no intimal arteritis is present, but there are foci of mild tubulitis (1 to 4 mononuclear cells/tubular cross section) and at least i1.
4. Acute/active rejection
  - TYPE IA - Cases with significant interstitial infiltration ( $> 25\%$  of parenchyma affected) and foci of moderate tubulitis ( $> 4$  mononuclear cells/tubular cross section or group of 10 tubular cells).
  - TYPE IB - Cases with significant interstitial infiltration ( $> 25\%$  of parenchyma affected) and foci of severe tubulitis ( $> 10$  mononuclear cells/tubular cross section or group of 10 tubular cells).
  - TYPE IIA - Cases with mild to moderate intimal arteritis (v1).
  - TYPE IIB - Cases with severe intimal arteritis comprising  $> 25\%$  of the luminal area (v2).
  - TYPE III - Cases with "transmural" arteritis and/or arterial fibrinoid change and necrosis of medial smooth muscle cells (v3 with accompanying lymphocytic inflammation).
5. Chronic/sclerosing allograft nephropathy\*\*
  - GRADE I (Mild) Mild interstitial fibrosis and tubular atrophy without (a) or with (b) specific changes suggesting chronic rejection.
  - GRADE II (Moderate) Moderate interstitial fibrosis and tubular atrophy (a) or (b).
  - GRADE III (Severe) Severe interstitial fibrosis and tubular atrophy and tubular loss (a) or (b).
6. Other, specify (changes not considered to be due to rejection, i.e., post-transplant lymphoproliferative disorder, nonspecific changes, acute tubular necrosis, etc.)

\*The recommended format of report is a descriptive narrative signet followed by numerical codes (Banff 97) in parentheses. Categorization should in the first instance be based solely on pathologic changes, and then integrated with clinical data as a second step. More than one diagnostic category may be used if appropriate.

\*\*Glomerular and vascular lesions help define type of chronic nephropathy; chronic/recurrent rejection can be diagnosed if typical vascular lesions are seen.

